APPENDIX F: Decision Conflict Scale

Cancer treatments sometimes impact fertility and may change the options you have for having a child.

Family-building after cancer may require assisted reproductive technology, such as in vitro fertilization (IVF), surrogacy, or adoption.

The decision of how you want to pursue family-building can be difficult to think about. There are often “pros” or positive aspects (benefits) of pursuing one option over another, as well as “cons” or negative aspects (sometimes thought of as risks or side effects).

We would like to know how you feel about the decision of whether or not to undergo fertility preservation in the future.

	Neither Strongly disagree					Strongly disagree, nor agree					Strongly agree				
1. I know which options are available to me.															
2. I know the benefits of each option.															
3. I know the risks and side effects of each option.															
4. I am clear about which benefits matter most to me.															
5. I am clear about which risks and side effects matter most to me.															
6. I am clear about which is more important to me (the benefits or the risks and side effects).															
7. I have enough support from others to make a choice.															
8. I am choosing without pressure from others.															
9. I have enough advice to make a choice.															
10. I am clear about the best choice for me.															
11. I feel sure about what to choose.															
12. This decision is easy for me to make.															
13. I feel I have made (or could make) an informed choice.															
My decision shows (or would show) what is important to me.															
14. I expect to stick with my decision. □ NA – I have not made a decision.															
15. I am satisfied with my decision. □ NA – I have not made a decision.															

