5.0 STATISTICAL CONSIDERATIONS

5.1 Measurements

The following measures will be used. Note that assessments conducted only at baseline will not be reported as ClinicalTrials.gov outcomes.

	Timepoint		
	T1: baseline; pre-intervention	T2: 1-month post-baseline	T3: 3-months post-baseline
Primary			
Decision Conflict Scale (Appendix F): ²³ Validated, 16-item measure that assesses personal uncertainty in making a healthcare decision, modifiable factors contributing to uncertainty, and the quality of the decision made. It is valid, reliable, and responsive to change, and the most widely used measure of decision-making quality. Five subscales include: Informed, Values clarity, Support, Uncertainty, and Effective decision. Answers are on a 5-point scale from "Strongly agree" to "Strongly disagree." Scores are transformed to a 0 [no decisional conflict] to 100 [extremely high decisional conflict] scale such that higher scores indicate a worse outcome. Scores lower than 25 are associated with implementing decisions; whereas score exceeding 37.5 are associated with decision delay or feeling unsure about implementation.	X	X	X
Secondary			
Unmet fertility information needs (Appendix G): Investigator-designed questions (5 items) will assess perceived information needs about fertility and family-building topics. Participants will indicate (yes/no) whether they have as much information as they want about Risk of infertility, Risk of early menopause, Options to assess their fertility status, Options to preserve fertility, and Options for alternative family-building. Our prior use of this measure yielded adequate internal consistency ($\alpha = .81$). ⁷ Each item is answered 0-No or 1-Yes and total scores range from 0 to 5. Higher scores indicate better perceived knowledge (better outcome).	X	X	X

	Timepoint		
	T1: baseline; pre-intervention	T2: 1-month post-baseline	T3: 3-months post-baseline

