5.3 Sample size

The target sample size is 100.

Power Estimate: With a projected 20% attrition rate, we expect 80% power to detect an effect size of 0.3 for the T1-T2 change in DCS, with a two-sided paired t-test with a 0.05 significance level. We based this on a decision aid intervention for fertility preservation,³⁴ which reported 14% attrition and DCS means at baseline ($M = 51.6$, $SD = 32.8$) and 1-month post-intervention ($M = 16.6$, $SD = 26.5$). We assumed the same DCS baseline mean, but were conservative and assumed higher attrition, higher DCS mean at follow-up ($M = 40$, $SD = 26.5$), and correlation coefficient between measurements to be 0.3, so that the effect size will be 0.33; representing a moderate effect size based on Cohen’s taxonomy. This also follows the DCS manual.

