5.4 ClinicalTrials.gov Outcomes

Similar to endpoints, ClinicalTrials.gov outcomes are assessments that evaluate the Roadmap to Parenthood intervention. Following are the ClinicalTrials.gov outcome titles; descriptions, and timeframes.

Outcome 1 (Primary)

Title: Decisional Conflict Scale (DCS)

Description: The Decisional Conflict Scale (DCS) is a validated survey that assesses personal uncertainty in making healthcare decisions; modifiable factors contributing to uncertainty; and the quality of the decision made. It is reliable and responsive to change, and the most widely used measure of decision-making quality. The survey has 16 questions, with responses on a 5-point scale ranging from “strongly agree” (1) to “strongly disagree” (5). Total scores range from 16 to 80, with higher scores indicating greater uncertainty (worse outcome). The outcome will be reported as the mean difference from baseline to 1 and 3 months, with standard deviation.

Timeframe: 3 months

Outcome 2 (Secondary)

Title: Unmet Fertility Information

Description: This investigator-designed survey assesses perceived information needs about fertility topics such as the risk of infertility; risk of early menopause; options to assess fertility status; options to preserve fertility; and options for alternative family-building. The survey has 5 questions, each answered by a Yes / No response. Yes is scored as 1, and no is scored as 0. Total scores range from 0 to 5, with higher scores indicating greater perceived knowledge. The outcome will be reported as the mean difference from baseline to 1 and 3 months, with standard deviation.

Timeframe: 3 months

Outcome 3 (Secondary)

Title: Illness Perceptions Questionnaire-Revised (IPQ-R)

Description: The Illness Perceptions Questionnaire-Revised (IPQ-R) is a survey that assesses cognitive and emotional representations of illness and is validated in cancer populations. The survey has 28 questions, answered on a 5-point scale ranging from “strongly disagree” (1) to “strongly agree” (5). Total scores range from 28 to 140, with higher scores indicating worse outcomes. The outcome will be reported as the mean difference from baseline to 1 and 3 months, with standard deviation.

Timeframe: 3 months

Outcome 4 (Secondary)

Title: Reproductive Concerns After Cancer (RCAC) Scale

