APPENDIX E, Reproductive History
Post-treatment Follow-up Care

After you finished your cancer treatment...

9. Has your oncologist or other health care professional discussed fertility with you during your follow-up care?

Yes, I was satisfied with the amount of information I received
 Yes, but I was NOT satisfied with the amount of information I received
 No, it was not discussed at all
 No, I was not interested in receiving this information, or it was not applicable to me
 I don't remember

10. Has your oncologist or other health care professional discussed risk for infertility or premature menopause with you during your follow-up care?

Yes, I was satisfied with the amount of information I received
 Yes, but I was NOT satisfied with the amount of information I received
 No, it was not discussed at all
 No, I was not interested in receiving this information, or it was not applicable to me
 I don't remember

11. Has your oncologist or other health care professional discussed fertility preservation or alternative family-building options (such as adoption) with you during your follow-up care?

Yes, I was satisfied with the amount of information I received
 Yes, but I was NOT satisfied with the amount of information I received
 No, it was not discussed at all, but I wish it had been
 No, I was not interested in receiving this information, or it was not applicable to me
 I don't remember

12. Have you been referred to a fertility specialist or reproductive endocrinologist since your treatment ended?

Yes, I was referred and I have met with a fertility specialist or reproductive endocrinologist (but have not pursued fertility preservation)
 Yes, I was referred but I have NOT met with a fertility specialist or reproductive endocrinologist
 No, I was not referred, but I am interested in this
 No, I was not referred, but I pursued it on my own
 No, I was not referred and I am NOT interested in this
 I don't remember or am unsure.

13. Have you met with a fertility specialist or reproductive endocrinologist since your treatment ended?

Yes

No

A fertility evaluation is generally done by a reproductive endocrinologist, a gynecologist who specializes in fertility. Blood is drawn to measure fertility hormone levels and an ultrasound is done so the doctor can see your ovaries.

14. Have you undergone a fertility evaluation with a reproductive specialist since your cancer treatment ended?

Yes → go to Question 35

No → go to Question 34

Unsure → go to Question 34

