Appendix G. Unmet Information Needs

Many cancer survivors want information about their fertility. Do you feel you have as much information as you want about the topics below?

			Not	Prefer not
	Yes	No	Interested	to answer
1. My risk of infertility	—	—	—	—
2. My risk of early menopause	—	—	—	—
3. Options to assess my fertility status	—	—	—	—
4. Option to preserve my fertility	—	—	—	—
5. Other options to build a family if I am not fertile	—	—	—	—

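### As printed, the primary outcome form (DCS, Appendix F) asks for ratings of a fertility preservation decision, which is narrower than the family-building decision the website is meant to support

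*Combined protocol and SAP*

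**What the plan says.** Section 4.0 makes the DCS in Appendix F the primary outcome. Section 5.2 tests its mean change from T1 to T2 and reports Cohen's d. The form is given at T1, T2 and T3 (section 5.1, Appendix B).

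The stem of Appendix F first says that family-building after cancer may involve assisted reproduction, surrogacy or adoption. It goes on: "The decision of how you want to pursue family-building can be difficult to think about". It then mentions the pros and cons of choosing one route over another. Its last sentence, the only one that says what to rate, is: "We would like to know how you feel about the decision of whether or not to undergo fertility preservation in the future".

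The descriptions of the outcome are generic. Section 5.1 says the scale "assesses personal uncertainty in making a healthcare decision"; section 5.4 says it "assesses personal uncertainty in making healthcare decisions".

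Sections 1.0, 2.0 and 4.0 present the website as support for decisions about family-building after cancer; section 4.0 adds fertility options. Appendix B notes that the printed questionnaires only represent the online ones.

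**The concern.** The DCS is a generic instrument whose statements take their meaning from the decision named above them. Here the introduction and the instruction name different things. One is a choice among several routes to having a child. The other is a yes-or-no choice about one procedure.

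A participant weighing surrogacy against adoption has two ways to answer. She can follow the instruction literally and rate preservation, or she can infer from the introduction that family-building was meant. Some eligible women may regard preservation as settled or not applicable: section 3.2 admits women after surgery affecting the reproductive organs, and Appendix E asks whether preservation has already been done. Appendix F has no box for that situation.

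At stake is what the primary effect size refers to. Objective 2 is to obtain a preliminary effect size for this decision aid. If the ratings concern a narrower decision than the aid targets, the estimate answers a narrower question. Objective 1 and the other measures are not touched.

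**Working it through.** The plan gives no figure on this point, so there is none to reproduce. The check compares the places where the rated decision is, or could be, named.

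1. **Stem, introduction (Appendix F).** Family-building: assisted reproduction, surrogacy, adoption. Fertility preservation has not been mentioned by this point.
2. **Stem, rating instruction (Appendix F).** Whether to undergo fertility preservation in the future.
3. **Statements (Appendix F).** They refer to options, each option, a choice, or this decision. None names preservation or family-building, so they do not settle the matter.
4. **Outcome descriptions (sections 5.1 and 5.4).** Healthcare decisions in general. They do not settle it either.
5. **Target of the website (sections 1.0, 2.0, 4.0).** Family-building after cancer, with fertility options included.
6. **A neighbouring measure.** The Stage of Decision-making form (headed Appendix T) does name its subject: several options for family-building.

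So the only explicit instruction names preservation, and nothing outside Appendix F confirms that choice.

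**How the two decisions relate.** Appendix E asks whether a professional "discussed fertility preservation or alternative family-building options (such as adoption) with you". Appendix G lists "Option to preserve my fertility" and "Other options to build a family if I am not fertile" as separate items. The words for alternative and other options are compatible with preservation being one route among several. These places therefore support calling the instruction narrower than the target. They do not show that it is unrelated to the target.

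**How much of the outcome sits under the stem.** Appendix F prints 15 numbered statements and 1 unnumbered: 15 + 1 = 16.

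- Maximum per participant completing all three surveys: 16 x 3 timepoints = 48 ratings.
- Items 14 and 15 each carry a box for not having made a decision. If both are marked every time: (16 - 2) x 3 = 14 x 3 = 42 ratings.

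These counts show only that the whole primary outcome depends on the stem. They do not measure error. The documents give no data on how participants read the stem, so no shift in the T1-T2 mean, in Cohen's d or in power can be calculated.

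**The case against.** The strongest reply is that preservation belongs to the subject. Section 4.0 describes a tool covering fertility as well as family-building options, and the wording in Appendices E and G can be read as placing preservation among the routes to a family. This stands: the fault is a narrower decision, not a foreign one.

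A second reply is that context repairs the slip. The sentences before the instruction are about family-building, and the first three statements ask about options in the plural, so many participants may answer about family-building anyway. This also stands, to the extent that no mismeasurement has been shown. It does not remove the conflict, because the explicit instruction still says otherwise and the plan does not say which reading is intended.

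Third, the fielded form may differ from the printed one, as Appendix B allows. That limits the point to the printed text and makes checking the live form the first step.

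Two stronger readings are tempting. A reader might infer from section 5.3, which says "We based this on a decision aid intervention for fertility preservation", that the DCS here is deliberately a measure of conflict about preservation. Section 5.3 borrows planning values and does not define the rated decision; sections 1.0, 2.0 and 4.0 point to family-building. A reader might also infer that the primary result will be biased or underpowered. Nothing in the documents allows either to be shown.

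**Conclusion.** The point holds for the form as printed. The instruction of the primary outcome names a narrower decision than its own introduction and than the website's target, and neither the statements nor sections 5.1 and 5.4 resolve this. The T1-T2 effect size may therefore not describe the decision the aid is meant to support.

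It should be fixed, because it concerns what the primary outcome refers to. It is confined to the interpretation of the DCS part of Objective 2. Between 42 and 48 ratings per participant with complete follow-up fall under the stem; the effect on the result is unknown. The conclusion assumes that the live REDCap stem matches Appendix F.

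**What to change.** 1. Compare the stem in the live REDCap form with Appendix F.
2. If they match, replace the last sentence of the stem with one naming the family-building decision, for example: *Please rate the statements below with your decision about how to build a family after cancer in mind.* Use it unchanged at T1, T2 and T3, and name the same decision in the DCS descriptions in sections 5.1 and 5.4.
3. If data have already been collected under the present wording, do not change it between timepoints for any participant. Limit the DCS conclusion to the decision actually asked about, and report the ambiguity as a limitation.

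The cost is a check of the form, one sentence in the stem, a matching phrase in two sections and an IRB modification. No patients, visits or data items are added. There is one small downside: the planning means and standard deviations come from a fertility preservation study, so the new stem moves the measure slightly away from that benchmark. The gain is a single, clearly named decision; the edit is not expected to make the scale more sensitive.

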Appendix G. Unmet Information Needs

Many cancer survivors want information about their fertility. Do you feel you have as much information as you want about the topics below?

			Not	Prefer not
	Yes	No	Interested	to answer
1. My risk of infertility	—	—	—	—
2. My risk of early menopause	—	—	—	—
3. Options to assess my fertility status	—	—	—	—
4. Option to preserve my fertility	—	—	—	—
5. Other options to build a family if I am not fertile	—	—	—	—

APPENDIX H: Illness Perceptions Questionnaire (revised)

[questions will be adapted for YA-Fs' with a confirmed infertility diagnosis vs infertility risk]

We are interested in your own personal views of your fertility and reproductive health. Please indicate how much you agree or disagree with the following statements by ticking the appropriate box.

These questions refer to your possible risk for fertility problems, infertility, or premature menopause because of the cancer treatment you received.

This is NOT based on your individual risk and does NOT mean that you have or will have fertility problems in the future.

	Strongly Disagree	Disagree	Neither Disagree or Agree	Agree	Strongly Agree
1. My fertility is a serious problem.					
2. Problems related to my fertility have major consequences on my life.					
3. Problems with my fertility do not have much effect on my life.					
4. Problems with my fertility strongly affect the way others see me.					
5. Problems related to my fertility and/or family-building have (or will have) serious financial consequences.					
6. Problems related to my fertility and/or family-building cause difficulties for those who are close to me.					
7. There is a lot which I can do to control problems related to my fertility and/or family-building.					
8. What I do can determine whether my fertility and/or family-building problems get better or worse.					
9. Whether or not I experience problems related to my fertility and/or family-building depends on me.					

10. Nothing I do will affect the problems I experience (or may experience) related to my fertility and/or family-building.

11. I have the power to influence any problems that I experience (or may experience) with my fertility and/or family-building.

12. My actions will have no effect on my fertility and/or family-building.

13. There is very little that can be done to improve my fertility and/or family-building.

14. There are treatments that will be effective in curing any fertility problems that I might have now or in the future.

15. The negative effects of any fertility problems I experience now or in the future can be prevented (avoided) by treatments.

16. There are treatments that can address any fertility problems that I might experience.

17. If I experience fertility and/or family-building problems, there is nothing that can help.

18. The symptoms of fertility problems are puzzling to me.

19. My fertility is a mystery to me.

20. I don't understand my fertility or the problems I might have now or in the future.

21. My fertility doesn't make any sense to me.					
22. There is nothing that can help my risk for experiencing fertility and/or family-building problems.					
23. I get depressed when I think about my fertility and/or family-building.					
24. When I think about my fertility I get upset.					
25. My fertility makes me feel angry.					
26. My fertility does not worry me.					
27. The possibility that I might have fertility and/or family-building problems makes me feel anxious.					
28. I feel afraid when I think about my fertility and/or family-building problems .					

APPENDIX I: Reproductive Concerns after Cancer (RCAC) Scale

Thinking about how you feel right now about having (more) biological children someday, please circle whether you strongly disagree, somewhat disagree, neither agree nor disagree, somewhat agree, or strongly agree with each statement. If you feel that a statement does not apply to you, please select "Neither Agree nor Disagree".

	Strongly disagree	Somewhat disagree	Neither disagree, nor agree	Somewhat agree	Strongly agree
1. I am afraid I won't be able to have any (more) children.					
2. I am worried about passing on a genetic risk for cancer to my children.					
3. I worry about telling my (potential) spouse/partner that I may be unable to have children.					
4. I am scared of not being around to take care of my children someday.					
5. I can accept it if I'm unable to have (more) children.					
6. I am overwhelmed by the thought of trying to get pregnant (again).					
7. I am concerned that my (potential) spouse/partner will be disappointed if I can't get pregnant.					
8. I am worried about my ability to get pregnant (again).					
9. I am worried about how my family history might affect my children's health.					
10. I will be happy with life whether or not I have (more) children someday.					

	Strongly disagree	Somewhat disagree	Neither disagree, nor agree	Somewhat agree	Strongly agree
11. Having (more) children will make me more nervous about getting cancer again.					
12. I worry that getting pregnant (again) would take too much time and effort.					
13. I am cautious about having (more) children because I might not be around to raise them.					
14. It is stressful to think about trying to get pregnant (again).					
15. I will feel content if I do not have (more) children.					
16. The thought of telling my (potential) spouse/partner that I may be unable to have children makes me uncomfortable.					
17. I am concerned that I may not be able to have (more) children.					
18. I am afraid my children would have a high chance of getting cancer.					

APPENDIX J: Impact of Events Scale (revised)*

Below is a list of difficulties people sometimes have after stressful life events. Please indicate how distressing each difficulty has been for you. Please answer in regards to your feelings DURING THE PAST SEVEN DAYS.

Please answer with respect to your fertility and possible risk for experiencing problems with family-building.

		Not at all	A little bit	Moderately	Quite a bit	Extremely
1.	Any reminder brought back feelings about it.	0	1	2	3	4
2.	I had trouble staying asleep.	0	1	2	3	4
3.	Other things kept making me think about it.	0	1	2	3	4
4.	I felt irritable and angry.	0	1	2	3	4
6.	I thought about it when I didn't mean to.	0	1	2	3	4
9.	Pictures about it popped into my mind.	0	1	2	3	4
10.	I was jumpy and easily startled.	0	1	2	3	4
14.	I found myself acting or feeling as though I was back at that time.	0	1	2	3	4
15.	I had trouble falling asleep.	0	1	2	3	4
16.	I had waves of strong feelings about it.	0	1	2	3	4
18.	I had trouble concentrating.	0	1	2	3	4
19.	Reminders of it caused me to have physical reactions, such as sweating, trouble breathing, nausea, or a pounding heart.	0	1	2	3	4
20.	I had dreams about it.	0	1	2	3	4
22.	I tried not to talk about it.	0	1	2	3	4

*Only the Intrusive Thoughts and Avoidance subscales of the IES-R are included.

